Definitions and Reporting of Adverse Events

Definitions

Adverse Events:

Any undesirable clinical occurrence in a subject, whether it is considered to be study
medication related or not, that includes a clinical sign, symptom, or condition; and/or an
observation of an unintended technical procedural error.

Expected:

An adverse event is expected when the specificity and severity of the event is consistent with
a complication that is not related to the study specific medications or procedural technique,
but may be related to the surgical procedure

Unexpected:

• An adverse event is unexpected when the specificity or severity of an adverse event is not consistent with the standard. It refers to an adverse event that has not been observed before

Adverse Study Medication Event:

• A clinical sign, symptom or condition that is causally related to the product, administration of the product, or performance of the product.

Serious Adverse Event:

- Any untoward medical occurrence that:
 - Results in death,
 - Is life threatening,
 - Requires inpatient hospitalisation or prolongation of hospitalisation,
 - Results in persistent or significant disability/incapacity,
 - May have caused a congenital anomaly/birth defect,
 - Requires intervention to prevent permanent impairment or damage,
 - Is a medically important event or reaction.

IRAD Study Study Study Protocol

Reporting of Events

Adverse Events:

Any adverse event that occurs at any point in time from the beginning of the surgical procedure until either the participant is terminated from the study, or 7 days post-completion, should be recorded as follows:

- All information on general medical, operative, and study medication related complications (adverse events) will be documented on Case Report Forms.
- Information should include date of occurrence, description, severity, relationship to study medication, treatment, and date of resolution.
- The investigator will determine if the event is related to the study medication.
- Any adverse event in a study patient must be monitored until it has resolved or been considered non-clinically significant by the investigator.

Expected Events:

Should be reported to the principal investigator as soon as possible, but not later than five working days after the investigator first learns of the event

Adverse Study Medication Events

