Study staff will ensure that any adverse study medication events which occur will be documented and immediately reported to the principal investigator. They should also be reported to the reviewing Ethics Committee and institution as soon as possible, no later than fifteen working days after the investigator learns of the event. An evaluation of the adverse events will be conducted by the investigator. Following this, if it is determined that the adverse effect presents an unreasonable risk to participants, the trial will be terminated as soon as possible. Termination shall occur no later than five working days after the investigator makes the determination, and no later than fifteen working days after the investigator first receives notice of the adverse event.

Serious Adverse Events (SAEs)

Any adverse event considered to be serious in nature which occurs at any time point from signing of Informed Consent Form until either the patient is terminated from the study, or 7 days post-completion, should be recorded as follows:

- All SAEs should be reported immediately to the principal investigator no later than 24 hours after becoming aware of the event.
- This will be followed promptly by detailed, written reports.

• The investigator should comply with the applicable regulatory requirement(s) related to the reporting of serious unexpected adverse study medication reactions to the regulatory authority (MedSafe NZ) and the Ethics Committee.

 All other SAEs not related to the study medication will be reported to the Ethics Committee as directed.

Ethics Committee

Approval

The investigator is responsible for obtaining Ethics Committee and Governance approval to conduct this study

Prior to Initiation of the Study

Written approval by the Ethics Committee and Governance must be obtained prior to beginning the study. Discussions may be had with prospective participants regarding the study, however written Patient Informed Consent must not be obtained. Until all approvals are granted, study procedures must also not be performed on prospective study participants.

Progress Reports

Progress reports on the trial will be submitted by the investigator at the request of the Ethics Committee.

Final Reports

Upon completion of the investigation, each investigator will submit an Ethics Close-Out Report on his/her part of the investigation within three months of completion of the investigation. This will be submitted to the Ethics Committee.

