IO access has potential risks. The inability to inject at the site indicates incorrect placement of the needle (not in the medullary space). Extravasation into soft tissues is the most common complication, commonly caused by cortical disruption from multiple attempts into the same site, dislodging of the needle into the soft tissues or misplacement. This may lead to other complications such as compartment syndrome, cellulitis, osteomyelitis, fat embolism, inability to remove IO needle. These complications are rare, with an overall incidence of <1% [4].

There are 4 main complications of intraosseous infusion that have been reported in adults. All relate to technical errors or prolonged infusions in an emergent setting, and are therefore extremely unlikely to occur in the single, controlled injection proposed in this study.

1) Extravasation of fluid (due to incorrect needle placement)

This complication occurs when a needle is not placed correctly (outside the bone), and infusion of fluid or medication is commenced. With modern intraosseous needles this complication is reduced by closely monitoring the patient, particularly at the IO needle insertion site, and using appropriate length IO needles to prevent over penetration through the bone. The reported success rates for the EZ-IO needle used in the current study range from 94-100%, and it is anticipated that as the needle will be placed by a trained orthopaedic surgeon in a controlled theatre environment the chance of incorrect needle placement will be very low.

2) Compartment Syndrome

Compartment syndrome again relates firstly to incorrect needle placement and has been described rarely in an isolated case report following intraosseous infusions [27]. It occurs if the tip of the needle is placed into soft tissues rather than bone, then prolonged infusion of fluids is commenced without recognition of the situation, leading to increased pressures within tissues. Llarge published series of intraosseous infusions have not reported this complication suggesting it is very rare [26]. It is extremely unlikely to occur in the context of this study as the needle is left in situ for a very short time, and fluid is injected as a single bolus so needle malposition or fluid leakage into the tissue will be immediately recognised.

3) Fracture

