Appendix 2: NSAIDs and Voltaren™

Non-Steroidal Anti-Inflammatories

NSAIDs are antipyretic, anti-inflammatory, and analgesia agents, typically divided into groups based on their chemical structure and selectivity. Broadly they can be characterised into non-selective NSAIDs (COX-1 and COX-2) and COX-2 selective NSAIDs. NSAIDs mainly act by inhibiting the enzyme cyclooxygenase (COX) which is required in the production of prostaglandins and other eicosanoids, resulting in the mitigation of pain, fever, and inflammation [12, 13]. The two groups have slightly different side effect profiles due to their different selectivities.

The adverse effect profile of NSAIDs is well known and can affect multiple organ systems. Most importantly, COX-1 is heavily involved in maintaining gastric mucosal integrity and COX-2 is primarily involved in the process of inflammation. Theoretically, COX-2 inhibitors should provide the same anti-inflammatory effects while reducing gastric adverse effects [13]. Gastrointestinal (GI) side effects may include nausea, vomiting, diarrhoea, dyspepsia, abdominal pain, GI ulcers, GI bleeding. Regarding cardiovascular events, all NSAIDs have an increased risk of hypertension, myocardial infarction, heart failure, stroke (and death). Other adverse effects include reduced renal perfusion and subsequent acute kidney injury, liver enzyme derangement (hepatotoxicity and hepatitis are rare consequences), and an increased risk of bleeding due to impaired platelet aggregation. As with any other medication, there is also the risk of anaphylaxis [12, 13]. Hence, it is desirable to avoid these systemic side effects, and regional administration allows us to do so by maximising local analgesia at the surgical site while minimising side effects.

Voltaren™ (Diclofenac)

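### The Expected and Unexpected definitions leave the protocol's own listed complications without a clear class, and a non-serious cannula event may have no reporting deadline

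*Protocol*

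**What the plan says.** The section Definitions and Reporting of Adverse Events sets up three classes below the serious adverse event (SAE).

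- **Expected:** consistent with "a complication that is not related to the study specific medications or procedural technique", although it may be related to the surgery.
- **Unexpected:** two sentences. The first reads "An adverse event is unexpected when the specificity or severity of an adverse event is not consistent with the standard". The second reads "It refers to an adverse event that has not been observed before".
- **The third class, Adverse Study Medication Event,** rests on causality alone and is worded as "A clinical sign, symptom or condition that is causally related to the product, administration of the product, or performance of the product". There is no expectedness test.

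The reporting rules attach to these classes.

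- Expected events go to the principal investigator "not later than five working days after the investigator first learns of the event".
- Adverse study medication events go to the principal investigator immediately, and to the Ethics Committee and institution within 15 working days. They are then evaluated, and that evaluation can lead to termination of the trial.
- All SAEs go to the principal investigator within 24 hours. The investigator is to comply with applicable requirements on the "reporting of serious unexpected adverse study medication reactions to the regulatory authority (MedSafe NZ) and the Ethics Committee". SAEs not related to the study medication go to the Ethics Committee as directed.

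The appendices list harms that are already known. Appendix 1 says "Extravasation into soft tissues is the most common complication" and describes four main complications of intraosseous infusion: extravasation, compartment syndrome, fracture and infection. Appendix 2 lists gastrointestinal, cardiovascular, renal, hepatic and bleeding effects of NSAIDs, and adds "As with any other medication, there is also the risk of anaphylaxis".

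**The concern.** Expectedness normally asks whether an event of that kind and severity is already described in a reference list. Relatedness is a separate question. The protocol merges the two: an event counts as expected only if it is unrelated to the drug and technique. That removes from Expected exactly the harms that Appendices 1 and 2 warn about, while the second Unexpected sentence keeps them out of the opposite class because they have been seen before.

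Two things are at stake. First, the regulatory line turns on the word unexpected, and staff have two tests for that word that can give opposite answers. Second, the deadlines and the termination evaluation are attached to named classes, so an event that fits no class has no deadline and no formal evaluation. The protocol calls the procedure novel, so events arising from the intraosseous access are ones it should be able to place without argument.

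**Working it through.** No arithmetic underlies the definitions. The check takes representative events through each definition and then through the reporting rules.

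| Event | Expected? | Unexpected, test 1 (differs from the standard) | Unexpected, test 2 (never observed) | Study medication event? | Reporting stated |
|---|---|---|---|---|---|
| Complication of the surgery only | Yes | n/a | n/a | No | Principal investigator, 5 working days |
| Known NSAID reaction, related, non-serious | No: related | Undecidable: standard not defined | No | Yes | Principal investigator immediately; Ethics Committee and institution, 15 working days |
| Known NSAID reaction, related, serious, unusually severe | No: related | Yes, on severity | No | Yes | As above, plus principal investigator within 24 hours; regulatory line unclear |
| Extravasation of intraosseous diclofenac, attributed to its administration, non-serious | No: related | Undecidable | No | Yes | As for the known NSAID reaction |
| Serious cannula complication, not attributed to the product | No: technique | Undecidable | No | No | Principal investigator within 24 hours; Ethics Committee as directed |
| Non-serious cannula complication, not attributed to the product or its administration | No: technique | Undecidable | No | No | CRF record and follow-up; no deadline |

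Three results follow.

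1. **The two classes are not complementary.** Every related complication in Appendices 1 and 2 fails Expected and fails the second Unexpected test. The first test cannot settle the matter, because the standard it refers to is not defined.
2. **The two Unexpected tests conflict on severity.** In the third row the first test says yes and the second says no. The protocol does not say which prevails.
3. **One row has no deadline.** Deadlines exist for expected events, adverse study medication events and SAEs. The last row is none of these. The termination evaluation is placed under adverse study medication events, so this event is outside it too.

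The last row can arise in practice. The adverse event definition expressly includes unintended technical errors, so a needle problem is an adverse event. All 23 + 23 = 46 participants receive the cannula. In the 23 controls the intraosseous fluid is saline and then vancomycin, so attribution to the product is least natural there. The CRF items listed under Reporting of Events ask only about relation to the study medication, whereas Data Capture and Analysis plans a review of relevance to the procedure or intervention.

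Size of the residue, from Appendix 1's own figures:

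- Overall complication incidence below 1%: fewer than 0.01 × 46 = 0.46 events in the trial, and fewer than 0.01 × 23 = 0.23 in the control arm.
- Needle success of 94–100% means failed placement in 0–6%: 0 to 0.06 × 46 = 2.76 participants. A failed placement is not necessarily an extravasation, so this is an upper range for technical events, not a forecast of harm.

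**The case against.** The strongest reply is that the other routes already do most of the work, and much of it stands.

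- **Drug-related events lose nothing by missing the 5-working-day rule.** A reader might infer from the gap that their deadline is lost. It is not: the study medication event rule requires immediate reporting whatever the expectedness, which is stricter.
- **Missing the regulatory line is partly by design.** A route for serious unexpected reactions leaves out known reactions of known severity even when the definitions are well drafted, and would do so after the fix below. Only reactions of unusual severity are affected.
- **The regulatory route does not open solely for events never seen before.** That reading is tempting from the second Unexpected sentence. But the first sentence makes severity sufficient, nothing says the second overrides it, and the SAE section refers the investigator to external requirements. The wording is ambiguous, not exclusionary.
- **The comparison of harms between arms is not shown to be distorted.** A reader might suppose that identical needle events would be classed differently by arm. Surgeons and anaesthetists are blinded and the investigators are orthopaedic surgeons, so assessors would not know what the intraosseous syringe held. The planned comparison uses frequencies and logistic regression, not expectedness or the study medication event class.
- **Other safeguards exist.** Serious cannula complications reach the principal investigator within 24 hours. All events are recorded and followed, CRFs are checked for patient risk, and a Data Safety Committee is to review adverse event forms. A broad reading of administration of the product could also take in some needle events.

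These replies do not reconcile the definitions. Nor do they give the last row of the table a deadline or a place in the termination evaluation, unless staff adopt the broad reading, which the protocol does not state. Blinding also means that an assessor cannot cleanly apply a class that depends on whether the product was in the syringe.

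**Conclusion.** The point holds as a faulty stated rule with limited consequences. The Expected definition rests on absence of relation, the two Unexpected tests conflict, and the related complications in Appendices 1 and 2 therefore have no clear class. The line on serious unexpected reactions cannot be applied reliably to a known reaction of unusual severity. A non-serious cannula or technique complication not attributed to the product or its administration has no reporting deadline and is outside the evaluation that can lead to termination.

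The number of events affected is likely to be small: fewer than 0.46 complications of any seriousness across 46 participants if the incidence in Appendix 1 applies here. That figure assumes the protocol's below-1% rate covers all cannula complications, which its wording leaves open for extravasation. The conclusion on the definitions does not depend on it. It rests on a literal reading of the definitions and on taking the product to mean the study drug. The efficacy analysis is not touched. The change should be made because it concerns safety escalation for a novel technique and costs little.

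**What to change.** Reconcile the definitions and reporting rules with the two appendices:

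1. Define expectedness independently of causality. Expected means listed in Appendix 1, Appendix 2 or a short list of known total knee arthroplasty complications, and no more severe than described there. Unexpected means not listed, or more severe than listed. The lists then replace the undefined standard.
2. Delete the condition "a complication that is not related to the study specific medications or procedural technique" and the sentence "It refers to an adverse event that has not been observed before".
3. State that events related to the study medication, its placebo or the intraosseous access, in either arm, follow the adverse study medication event reporting and evaluation path. This also lets a blinded assessor classify an event without knowing the allocation.
4. Add one CRF item for relationship to the intraosseous access, beside the existing item on the study medication.

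The cost is a few sentences of protocol wording, with the Ethics Committee approval that any modification needs, and one CRF field. The small downside is that a few more events will follow the faster route.

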Multiple surgeons who regularly perform TKA will carry out this procedure on all patients included in the trial. Prior to all surgeries, each patient will undergo a general anaesthetic (GA) for their procedure, and no patients will have a neuraxial and/or peripheral nerve block. This will involve total IV anaesthesia with IV Propofol and IV fentanyl, as well as Ketamine and/or Clonidine in small amounts as adjuncts to the GA. The airway will be maintained via laryngeal mask airway. As part of usual TKA protocol 2g IV Cephazolin, 2g IV Tranexamic acid, and 16mg IV Dexamethasone will also be administered. The Patient will then be positioned appropriately for surgery and a single cuff tourniquet applied to the upper thigh of the marked limb. Following standard patient preparation

and draping of the appropriate limb, the limb is exsanguinated, and the tourniquet inflated to cease blood flow in the limb at 250-300 mmHg for the duration of the procedure (60-90 minutes). A proximal tibial IO cannula will then be inserted, and the study medication administered into bone immediately before skin incision [6, 7].

There will be two groups into which patients will be randomised; 23 patients will be randomised into each group:

- Group 1: IORA 75mg Diclofenac preoperatively (intervention group).
- Group 2: IV infusion 75 mg Diclofenac preoperatively (control group).

For the patients randomised to the IORA Diclofenac group, following tourniquet inflation a proximal tibial cannula will be inserted. The study medication will be administered via the cannula into bone immediately before skin incision. 75mg Diclofenac (75 mg/3 mL ampoules) will be made up to 10mL with normal saline 0.9% in a syringe to dilute the medication prior to administration. The medication will then be injected as a bolus by the blinded surgeon. Immediately after, 500 mg of Vancomycin in 110 mL normal saline 0.9% will be delivered intraosseously. These patients will also receive a preoperative IV infusion of 100 mL normal saline 0.9% over 2 minutes by the blinded anaesthetist. The infusion will finish at least 3 minutes prior to tourniquet inflation.

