The patients randomised into the second group will receive an IV infusion over 2 minutes of 75 mg Diclofenac (75 mg/3 mL ampoule) diluted to 100 mL with normal saline 0.9%, to finish at least 3 minutes prior to tourniquet inflation, by the blinded anaesthetist. Diclofenac (Voltaren™) 75 mg/3 mL solution has been approved by New Zealand Medsafe for intravenous infusion, but requires to be diluted. There are injectable Diclofenac formulations which can be administered as bolus, however these are not available in New Zealand. 10 mL of normal saline 0.9% will be given via IO after tourniquet inflation, followed by the same preparation of Vancomycin by the blinded surgeon.

An unblinded researcher (not the surgeon or anaesthetist) will prepare the medication as described above, according to the participant's group allocation. The preparation for IV infusion will be given to the blinded anaesthetist, and the preparation for IO injection will be given to the blinded surgeon.

All patients will also receive intraoperative local infiltration anaesthesia prior to skin closure in the form of 150 mL of 0.2% Ropivacaine with 0.3mcg of Adrenaline 1:1000 (0.3 mL). This is placed intra-articular and in the tissue surrounding the knee. Weight based dosage of ropivacaine will be used if patients are small.

Patients in all study groups will receive a standardised regimen of pain relief (unless certain medications are contraindicated) post-op as an inpatient and on discharge. Post-op analgesia includes IV Morphine 1-2 mg (in recovery only), Paracetamol 1 g PO QID, Celecoxib (dose will be prescribed according to weight/age), Tramadol modified release 100 mg PO BD, Gabapentin (dose will be prescribed according to weight/age), and Sevredol 10 mg PO Q1H PRN. The same preparation of Paracetamol, Celecoxib, Tramadol, and Gabapentin will be prescribed on discharge, but Sevredol will be reduced to 10 mg PO Q4H.

Informed Consent

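### General adverse event recording opens at an undefined start of surgery, which on two of three readings leaves study drug administration outside the window

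*Protocol*

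**What the plan says.** Three recording rules in the Protocol bear on this point, and each has a different start.

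- General adverse events (Reporting of Events, Adverse Events): "Any adverse event that occurs at any point in time from the beginning of the surgical procedure", running to termination from the study or 7 days after completion. The opening point is not defined as anaesthesia, tourniquet inflation or incision.
- Serious adverse events (Serious Adverse Events): any such event "which occurs at any time point from signing of Informed Consent Form".
- Drug-related events (Adverse Study Medication Events): "any adverse study medication events which occur will be documented and immediately reported to the principal investigator". No start time and no seriousness threshold is given. The Definitions section describes such an event as "A clinical sign, symptom or condition that is causally related to the product, administration of the product", or performance of the product.

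The order of dosing is in the treatment description that follows the exclusion criteria. For the control arm: "The patients randomised into the second group will receive an IV infusion over 2 minutes of 75 mg Diclofenac", diluted to 100 mL, "to finish at least 3 minutes prior to tourniquet inflation, by the blinded anaesthetist". The intervention arm has a 100 mL saline infusion at that stage, with the same timing. Its diclofenac is injected through the tibial cannula after inflation and just before the skin is cut. General anaesthesia is described there as coming before surgery, and the Blinding section says patients are already anaesthetised when study drug is given.

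**The concern.** A recording window for adverse events should cover all study drug administration and should open at the same point relative to dosing in each arm. Here the general window is tied to a surgical milestone. The two arms receive their active dose at different times relative to that milestone, so the rule may cover one arm's dose and not the other's.

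The Data Capture and Analysis section plans adverse event frequencies and a logistic regression between the groups. The rationale section and Appendix 2 argue that regional delivery lessens systemic adverse effects. A rule that might omit early events in the systemic arm touches that comparison directly, and with 23 patients per arm one event more or less is visible. There is also no stated reason why serious events are collected from consent while non-serious ones wait for surgery.

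**Working it through.** The protocol states no figure to reproduce, and the only arithmetic is a timeline.

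**Inputs (treatment description):** infusion length 2 minutes; interval from end of infusion to tourniquet inflation at least 3 minutes, with no upper limit.

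**Timeline, taking inflation as time 0:**
- IV infusion ends at −3 minutes or earlier.
- IV infusion starts at −(3 + 2) = −5 minutes or earlier.
- Intraosseous cannulation and bolus come after 0 and immediately before incision.
- Skin incision follows.

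**Where each active dose falls under each reading of the start of surgery:**

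| Surgery begins at | Control IV dose | Intervention IO dose | IO cannulation (both arms) |
|---|---|---|---|
| Anaesthesia | inside | inside | inside |
| Tourniquet inflation | before window | inside | inside |
| Skin incision | before window | before window | before window |

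**Which reading does the text favour?**
- Anaesthesia is the least consistent with the wording, since the treatment description puts it before surgery.
- Inflation has some support: the tourniquet is said to stay up for the length of the procedure.
- Incision also has some support: the protocol calls the dose preoperative in both arms, including the intraosseous one given after inflation.

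The incision reading removes the difference between arms in whether the active dose is covered, but it leaves out the novel step. Appendix 1 names extravasation as the most common complication of intraosseous access and expects any leak to be noticed at once, that is, at injection.

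**Which events would be lost?** An event must meet all of these conditions to escape every rule:
1. It is non-serious; otherwise the rule running from consent applies.
2. Its onset lies between the start of study drug administration and the start of surgery. Reactions that first appear during or after surgery are inside the general window.
3. It is not attributed to study drug; otherwise the drug-event rule applies.

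The third condition is not remote. Patients cannot report symptoms, surgeon and anaesthetist are blinded, and propofol, fentanyl, cephazolin, tranexamic acid and dexamethasone are also part of the perioperative regimen. A brief rash or pressure change could reasonably be put down to one of those.

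**A label conflict to note.** The Blinding section assigns the diclofenac infusion to the intervention group and the saline infusion to the control group, the reverse of the treatment description. The timeline above follows the treatment description. The two places must be reconciled.

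**The case against.** The strongest reply is that drug reactions already have their own rule. Any adverse study medication event must be documented, with no start time and no seriousness threshold. A reader might infer from the general window that non-serious reactions to the control infusion go unrecorded. The text does not support that: a reaction recognised as drug related is covered whenever it occurs. This stands, and it shrinks the point considerably. It does not dispose of it, because that rule works only once someone has judged the event to be drug related, whereas the general definition of an adverse event applies regardless of cause.

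A reader might also infer that the control arm alone is undercounted and that the safety comparison is therefore biased. That follows only if surgery begins at tourniquet inflation. On the incision reading both arms are affected, and on the anaesthesia reading neither is.

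It is tempting, too, to assume a reaction rate and work out the chance of at least one event among 23 control patients. The protocol gives no such rate, and the result would be the chance that an event occurs, not that it goes unrecorded.

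Three further replies have some force. The form asks for the date of an event, not the clock time, so staff may in practice record events from just before surgery. The research team is charged with capturing complications not otherwise documented. Safety is not among the stated objectives or questions. These lower the stakes, but they rely on staff going beyond the written rule. Different start points for serious and non-serious events are not a contradiction in themselves.

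**Conclusion.** The point holds in a limited form and is minor. The start of the general window is undefined, and on the tourniquet and incision readings at least one arm's active dose is given before it opens: in the control arm by at least 5 minutes to the start of the infusion and at least 3 minutes to its end, measured to inflation. What is exposed is a small class of events: non-serious, with onset in that short interval, and not attributed to study drug. An arm difference in coverage of the active dose is possible but not established, since it depends on which milestone is meant. The size of any undercount cannot be derived from the protocol.

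The conclusion assumes that the dosing sequence in the treatment description is the intended one, despite the reversed infusion labels in the Blinding section, and that the drug-event rule is not itself limited by the general window, which the text does not say.

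**What to change.** In Reporting of Events, Adverse Events, replace the surgical milestone with an explicit start that is no later than the start of the preoperative IV study infusion, or with consent as for serious events, and apply it identically in both arms. Carry the same start into the case report form instructions. Separately, reconcile the infusion labels in the Blinding section with the treatment description.

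The cost is one sentence in the protocol, a matching line on the form, and a few more minor events recorded around induction. Sample size and the primary outcome are unaffected.
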